Study Objective(s)	Explore electrical field shape sensitivity and amplitude sensitivity in sub-perception SCS (anatomically-guided 1kHz stimulation) to obtain initial impressions of effect (i.e. not statistically powered based on a priori information about effect size).
Test Device	Boston Scientific Neuromodulation (BSN) Precision Spectra™ system with tightly spaced percutaneous lead(s)
Control Device	None; each patient will serve as their own control
Study Design	Prospective, postmarket, exploratory, multi-center, randomized, double-blinded (subject, evaluator blinded; programmer un-blinded)
Planned Number of Subjects	Approximately 10 patients to enter randomization phase
Planned Number of Investigational Sites / Countries	Up to two centers (United Kingdom)
Primary Endpoint	There is no primary endpoint. Collected data will be used to increase the understanding of the therapy, guide product development and help define the best practice for programming with 1KHz therapy
[REDACTED]	
 [REDACTED] [REDACTED] [REDACTED] [REDACTED] [REDACTED]

High Rate Spinal Cord Stimulation: Field Shape and Amplitude Sensitivity Exploratory Study (CONTOUR Study)	
	
█ [REDACTED]█ [REDACTED]█ [REDACTED]█ [REDACTED]
Method of Assigning Patients to Treatment	Subjects in whom an effective 1kHz bipole setting is found, will be randomized in an equal distribution to bipole or “Dorsal Horn Modulation” stimulation setting for 15 days, followed by a crossover to the opposite programming method for additional 15 days. Subjects in whom an effective 1kHz bipole setting was not found will continue participation in the study for 3 month follow-up period, under center’s standard of care SCS strategy.
Follow-up Schedule	
• Screening period (>7 days)• Baseline Visit• Implant visit (standard of care)• Bipole Search Visit (start of bipole search)• Bipole search (approx. 21±7 days)• Randomization Visit (end of bipole search)• Cross-over Visit (21±5 days post Randomization Visit)• Release Visit (21±5 days post Cross-over Visit)• End of study (90±14 days post Release Visit)
Study Duration	The entire study will take approximately 1 year to complete. Each patient will be enrolled for approximately 6 months.
Key Inclusion Criteria	[REDACTED]

High Rate Spinal Cord Stimulation: Field Shape and Amplitude Sensitivity Exploratory Study (CONTOUR Study)	
	
■ Documented average low back pain intensity of at least 6 out of 10 over 7 days during Screening (Numerical Rating Scale)■ Stable daily pain-related medication prescription and intake of ≤ 100mg morphine-equivalents■ Capacity to describe and rate pain intensity, complete study measurements, and use the study device (e.g. patient remote control, charger, paper and electronic diaries) (physician discretion)
Key Exclusion Criteria	
■ Presence of pain or psychological condition that in the opinion of the investigator may interfere with the subject's ability to rate their pain and communicate such ratings■ Previous Spinal Cord Stimulation trial or is already implanted with an active implantable device(s) (e.g. pacemaker, drug pump, implantable pulse generator)
Statistical Methods	
Primary Statistical Hypothesis	None
Statistical Test Method	Descriptive statistics will be employed in post-hoc analysis
Sample Size Parameters	Sample size not determined in prospective manner

3. Table of Contents

1. TITLE PAGE	1
2. PROTOCOL SYNOPSIS.....	4
3. TABLE OF CONTENTS.....	7
3.1. Table of Figures.....	10
3.2. Table of Tables	10
4. INTRODUCTION	12
4.1. Chronic Intractable Pain.....	12
4.2. Conventional Spinal Cord Stimulation	12
4.3. Sub-perception Electrical Stimulation	13
4.4. Dorsal Horn Modulation (DHM) Technique.....	13
4.5. 1 kHz Anatomically Targeted Sub-perception SCS.....	14
5. DEVICE DESCRIPTION.....	14
6. STUDY OBJECTIVES	16
7. STUDY ENDPOINTS	16
8. STUDY DESIGN	16
8.1. Scale and Duration.....	17
8.2. Treatment Assignment.....	18
8.2.1. Treatment and Control.....	18
8.3. Justification for the Study Design.....	18
9. SUBJECT SELECTION.....	18
9.1. Study Population and Eligibility.....	18
9.2. Inclusion Criteria	19
9.3. Exclusion Criteria	19
10. SUBJECT ACCOUNTABILITY.....	20
10.1. Point of Enrollment.....	20
10.2. Withdrawal.....	20
10.3. Enrollment Controls	21
11. STUDY METHODS	21

11.1. Data Collection	21
11.2. Study Candidate Screening	24
11.3. Informed Consent	24
11.3.1. Post-Consent Eligibility Validation	24
11.4. Screening Period (duration >7 days within 90 days prior to Implant procedure) ending with Baseline visit	24
11.5. Implant Procedure (Standard of Care)	24
11.6. Bipole Search Visit (after Implant procedure per center’s standard of care when healing period complete, duration 2-4 weeks)	25
11.7. Randomization Visit (21±7 days post Bipole Search Visit)	25

3.2. Table of Tables

Table 9.2-1: Inclusion Criteria.....	19
Table 9.3-1: Exclusion Criteria.....	20
Table 11.1-1: Data Collection Schedule	22
Table 11.16-1: Source Documentation Requirements	27
Table 20.2-1: Safety Definitions.....	37

Table 20.3-1: Criteria for Assessing Relationship of Study Device or Procedure to Adverse Event..... 38

Table 20.4-1: Investigator Reporting Requirements..... 41

Table 27.1-1: Abbreviations 48

Table 27.2-1: Definitions 48

4. Introduction

4.1. *Chronic Intractable Pain*

Chronic intractable pain is often defined as pain persisting for at least 6 months which has not responded to conservative treatment(s). The pain may be due to current or past nerve injury and causes significant disability, reduced work productivity, reduced quality of life, and significant cost burden. Early treatments for chronic pain typically include over the counter and prescription medications. Later treatments like physical therapy and interventional pain procedures (e.g. intraspinal injections, vertebroplasty, pulsed RF) are attempted, sometimes followed by chronic high dose opioids and back surgery, if indicated. If back surgery is unsuccessful in relieving the chronic pain, the patient can be labeled as having failed back surgery syndrome (FBSS). Spinal cord stimulation is an option in the well-selected patient with chronic low back and/or leg pain. Such pain can lead to a number of co-morbidities, including reduced health-related quality of life, reduced ability to engage in activities of daily living, increased disability, increased emotional depression, and weight gain due to the adoption of a sedentary lifestyle. Chronic low back and/or leg pain is typically categorized as either neuropathic, which involves pathological nerve activity and is commonly characterized by patients as ‘shooting’ or ‘burning’; nociceptive, which involves nerve signals indicating actual or impending tissue damage or inflammation (Grabois *et al.*, 2005); or a varying mixture of neuropathic and nociceptive pain.

4.2. *Conventional Spinal Cord Stimulation*

SCS is effective for chronic intractable pain associated with a variety of conditions, including, but not limited to, FBSS (Carter *et al.*, 2004, Taylor *et al.*, 2004), complex regional pain syndrome (Sears *et al.*, 2011), and low back pain and leg pain (Cameron *et al.*, 2004). Spinal cord stimulation (SCS) is a less invasive treatment option for FBSS but has generally been reserved for patients who have failed multiple, and indeed all possible, repeat operations. With SCS, an implanted pulse generator (IPG) delivers electrical current to electrode(s) implanted in the epidural space. This current stimulates nerves and can be programmed to direct stimulation to the nerves innervating the painful location, resulting in a reduction of the intensity of that pain (Kumar *et al.*, 2006). Before an SCS system is implanted, a patient often undergoes a screening trial with an electrode that is connected to an external stimulator that the patient wears outside of the body. The results of the screening trial can predict the patient’s outcome with an implanted system (Kumar *et al.*, 2006).

In SCS pain relief is realized when the nerves that innervate the painful region(s) are electrically stimulated (North *et al.*, 1990). To increase the chance of success, the electrode contacts are programmed based on the patient feedback about location of the stimulation induced paresthesia in response to various combinations of contact polarities (anodes and cathodes), pulse rate (or frequency), pulse amplitude (or current), and pulse width.

In an international multi-center RCT, Kumar *et al.* (2007) randomized 100 patients: 48 to conventional medical management alone (CMM group) and 52 to SCS plus CMM (SCS group). At 6 months, patients randomized to SCS achieved significantly greater pain relief and improved functional capacity and health-related quality of life compared with patients

randomized to CMM. Specifically, twenty four patients in the SCS group (48%) and four patients in the CMM group (9%) achieved the primary outcome of 50% leg pain relief ($p < 0.001$) at 6 months. This trend continued over the duration of 12 months as reported in Kumar 2007 with the SCS group experiencing improved pain relief, quality of life and functional capacity, as well as greater treatment satisfaction ($p \leq 0.05$). At 24 months (Kumar 2008), 37% of patients in SCS group continued to achieve at least 50% pain relief versus 2% of patients in the CMM group ($p = 0.003$). The results from the PROCESS study provide evidence that SCS is effective and cost effective in relieving chronic neuropathic pain associated with FBSS.

4.3. *Sub-perception Electrical Stimulation*

Traditionally, Spinal Cord Stimulation (SCS) has relied on the understanding that to achieve pain relief, dorsal column stimulation-induced paresthesia has to be generated around the area of pain in order to successfully treat pain (North et al. 1991). However, recent studies indicate that effective pain relief may be obtained by employing stimulation without paresthesia.

Van Buyten et al. (Van Buyten et al. 2012) reported the outcomes of a prospective, open-label, multicenter European clinical trial that utilized high frequency (up to 10 KHz) which did not produce paresthesia. Of 82 patients, 72 reported a significant improvement in VAS scores after trial and underwent permanent implantation. At six months, 74% of patients had a greater than 50% pain relief in back pain. Al-Kaisy et al. (Al-Kaisy et al., 2014) reported the long term outcomes of this cohort at 24 months – Mean back pain was reduced from 8.4 ± 0.1 at baseline to 3.3 ± 0.3 at 24 months ($p < 0.001$), and mean leg pain was reduced from 5.4 ± 0.4 to 2.3 ± 0.3 ($p < 0.001$). At 24 months, 60% of implanted patients had a greater than 50% pain relief in back pain.

DeRidder et al. (DeRidder et al 2010) reported the outcomes of a new stimulation paradigm (burst) used in 12 patients without paresthesia induction. During the trial period, an improvement of 5.25 points on VAS for axial pain for burst stimulation ($p < 0.001$) was reported versus a 1.83 points improvement for tonic stimulation. After more than 1 yr. of follow up, significant reduction in VAS scores for axial pain of 3.7 points and for limb pain of 5.15 points was noted with burst stimulation.

A randomized double-blinded comparison of high frequency SCS (HF SCS) and sham stimulation on patient's global impression of change, pain intensity and quality of life in existing SCS patients was conducted and reported by Perruchoud et al. (Perruchoud et al., 2013). Of 33 patients, the proportion of patients responding under HF SCS was 42.4% (14/33) versus 30.3% (10/33) in the sham condition. The mean benefit of HF vs. sham was not statistically significant.

4.4. *Dorsal Horn Modulation (DHM) Technique*

Traditional stimulation fields involve bipoles and tripoles which create localized concentrations of stimulation to evoke activity in the dorsal columns. Dorsal Horn Modulation Technique is a novel stimulation field which is designed to minimize stimulation of the dorsal column fibers and maximize stimulation of nerve fiber terminals that exist in the more lateral aspects of the cord (dorsal horn, dorsal root entry zone). It consists of a strip of cathodes whose individual amplitudes are calibrated according to the measured perception

thresholds from each contact. An algorithm takes the thresholds as inputs and outputs current percentages which are manually programmed.

4.5. 1 kHz Anatomically Targeted Sub-perception SCS

Similar to the experience with 10kHz SCS (see Van Buyten et al., 2012, Al-Kaisy et al., 2014), 1kHz subperception SCS has been reported to provide pain relief when programming is aimed at maximizing the overlap of pain with paresthesia when run at supraperception amplitudes (data unpublished).

The present study differs in that it targets the same anatomical target as traditional 10kHz SCS, namely the dorsal aspect of the epidural space overlying the region near the T9/T10 intervertebral disc, but using lower stimulation rates, namely 1kHz.

The purpose of this study is to explore field shape sensitivity and amplitude sensitivity in sub-perception SCS (anatomically-guided 1kHz stimulation) to obtain initial impressions of effects.

5. Device Description

The Precision Spectra™ System (Figure 5-1 and Figure 5-2) is an implantable neurostimulator system intended to aid in the management of chronic intractable pain.

The Precision Spectra™ System includes an implantable 32-contact, multi-channel pulse stimulator (IPG) with a rechargeable power source. Periodically, the implant battery is recharged transcutaneously by a Precision™ radiofrequency charging unit. The stimulator can accept up to 4 leads and support a maximum of 32 contacts. The Precision Spectra™ System can be used with any commercially available Boston Scientific SCS leads.

A 32-contact Precision Spectra™ External Trial Stimulator (ETS) is used to provide trial stimulation through the surgically placed leads prior to implantation of the implantable stimulator. The leads are connected to the trial stimulator by means of the Precision Spectra™ OR Cable during the trial period, which may occur intraoperatively (on-the-table trial).

A Clinician Programmer (CP) is provided to facilitate communication with, and programming of, the IPG and ETS. A programming Wand is used to provide a link between the Clinician Programmer and the ETS/IPG.

A hand-held battery operated Precision Spectra™ Remote Control provides the patient with the ability to access basic stimulator functions.

The Precision Spectra™ System uses the standard surgical tools and accessories for facilitating lead insertion and placement.

Figure 5-1: Precision Spectra™ Products and Accessories

[figure not shown]
IPG	ETS	OR Cables	Remote Control	Clinician Programmer	Wand
		 2x8 OR Cable  1x16 OR			

Figure 5-2: Implantable Neurostimulator System

The Precision Spectra™ System delivers current-controlled, asymmetrical biphasic charge-balanced electrical pulses to each contact. Patients control the amplitude of stimulation and turn stimulation on or off via a wireless handheld remote control. The available stimulation parameters are as follows: frequency 2 to 1200 Hz, pulse width 20 to 1000 μ sec, and amplitude 0-25.5 mA with a 12.7 μ C pulse charge limit.

All of the devices used in this study are commercially approved in Europe.

6. Study Objectives

The objective of this study is to explore electrical field shape sensitivity and amplitude sensitivity in sub-perception SCS (anatomically-guided 1kHz stimulation) to obtain initial impressions of effect.

7. Study Endpoints

[figure not shown]
Collected data will be used to increase the understanding of the therapy, guide product development and help define the best practice for programming with 1kHz therapy.

- [REDACTED]
- | [REDACTED]
 - | [REDACTED]
 - | [REDACTED]
 - | [REDACTED]
 - | [REDACTED]
 - | [REDACTED]
 - | [REDACTED]
 - | [REDACTED]
 - | [REDACTED]

8. Study Design

Prospective, postmarket, exploratory, multi-center, randomized, double-blinded (subject, evaluator blinded; programmer un-blinded) (Figure 8-1)

Figure 8-1: CONTOUR Study Design

8.1. Scale and Duration

The study will be conducted at up to two centers in UK. Approximately ten (10) patients will be randomized. Follow-up of each randomized patient will continue for 3 months after the randomization (cross-over) phase. Patients who complete all study measurements will participate in the study approximately 6 months from enrollment to their end of participation. The overall study may require up to one year to complete.

8.2. *Treatment Assignment*

Eligible patients who consent to participation and have met all of the inclusion and none of the exclusion criteria will undergo implant of the system. The subjects would undergo a 2-4 week period of 1 kHz bipole search. Those subjects in whom an effective bipole setting is found, will be randomized 1:1 to bipole stimulation followed by DHM for 15 days each, or DHM followed by bipole stimulation for 15 days each. After the crossover period, the subject enters into a 3 month follow-up period with the best of the two setting. Subjects for whom an effective 1 kHz bipole setting was not found will continue participation in the study for 3 month follow-up period, according to standard-of-care.

8.2.1. Treatment and Control

This study compares two stimulation field types: bipolar vs DHM, both at 1 kHz. The cross-over study design allows for comparing these treatments using one of the stimulation types as an active control.

8.3. *Justification for the Study Design*

The study design is prospective, postmarket, exploratory, multi-center, randomized, double-blinded (subject, evaluator; programmer un-blinded) study to obtain initial impression on the sensitivity to electrical field shape and amplitude in 1kHz anatomically-guided subperception spinal cord stimulation for chronic neuropathic pain treatment. It is exploratory because little is known about the best electric field and amplitudes to optimize subperception SCS. Due to the nature of sub-perception SCS, blinding is possible and will contribute to the strength of the evidence gathered from this study. Randomization will allow for controlling for order effect as previous research in subperception SCS has shown that the order effect can dominate the treatment effect (Perruchoud et al., 2013).

9. Subject Selection

9.1. *Study Population and Eligibility*

The study will include patients until approximately 10 have entered the randomization phase. Patients will generally be recruited from physician's practice and will be eligible to receive 1 kHz Spinal Cord Stimulation therapy to treat their chronic neuropathic pain condition in the legs and back using the commercially-approved Boston Scientific's Precision Spectra™ System per local DFU.

9.2. Inclusion Criteria

Subjects who meet all of the following criteria (Table 9.2-1) may be given consideration for inclusion in this clinical investigation, provided no exclusion criterion (see 9.3) is met.

Table 9.2-1: Inclusion Criteria

Clinical Inclusion Criteria	[REDACTED]
	[REDACTED]
	[REDACTED]
	[REDACTED] Documented average low back pain intensity of at least 6 out of 10 over 7 days during Screening (Numerical Rating Scale)
	[REDACTED]
[REDACTED] Stable daily pain-related medication prescription and intake of ≤ 100 mg morphine-equivalents	
[REDACTED] Capacity to describe and rate pain intensity, complete study measurements, and use the study device (e.g. patient remote control, charger, paper and electronic diaries) (physician discretion)	

Abbreviations: NRS – Numerical Rating Scale

9.3. Exclusion Criteria

Subjects who meet any one of the following criteria (Table 9.3-1) will be excluded from this clinical study.

Table 9.3-1: Exclusion Criteria

Clinical Exclusion Criteria	
[REDACTED] Presence of pain or psychological condition that in the opinion of the investigator may interfere with the subject's ability to rate their pain and communicate such ratings
 
[REDACTED] Previous Spinal Cord Stimulation trial or is already implanted with an active implantable device(s) (e.g. pacemaker, drug pump, implantable pulse generator)
 
[REDACTED]
 
[REDACTED]
 
[REDACTED]
 
[REDACTED]
 
[REDACTED]

------------------------------------	---

10. Subject Accountability

10.1. Point of Enrollment

A patient will be considered enrolled in this study after he/she signs and dates the informed consent form (ICF). No study-related procedures or assessments can take place until the informed consent form is signed.

10.2. Withdrawal

All subjects enrolled in the clinical study (including those withdrawn from the clinical study or lost to follow-up) shall be accounted for and documented. If a subject withdraws from the clinical investigation, the reason(s) shall be reported. The subjects who have withdrawn will continue to be followed per center's standard of care.

Reasons for withdrawal could include but are not limited to

- physician discretion
- patient choice to withdraw consent
- patient's failure to meet inclusion or not meet exclusion criteria after enrollment but prior to system implant
- failure to proceed to implantation with a BSC SCS IPG
- failure to be implanted with lead(s) at or near the region overlying the T9/10 intervertebral disc
- failure to achieve adequate pain relief during rescue period that follows the bipole search period
- lost to follow-up or
- death

While study withdrawal is discouraged, patients may withdraw from the study at any time, with or without reason, and without prejudice to further treatment.

All applicable case report forms (CRFs) up to the point of patient withdrawal and an “End of Study” form must be completed. Any patient deemed “lost to follow-up” should have a minimum of three documented attempts to contact him/her prior to completion of the “End of Study” form.

Additional data may no longer be collected after the point at which a patient has been withdrawn from the study or withdraws consent, for whatever reason. All open adverse events should be closed or documented as unresolved. Data collected up to the point of patient withdrawal may be used for study analysis.

Patients withdrawn prior to randomization will be replaced and will not be included in the site’s overall total for randomized patients.

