11.1. Data Collection

The data collection schedule is shown in Table 11.1-1.

Procedure/ Assessment	Screening Period (duration >7 days)	Baseline Visit	Implant Procedure (standard of care)	Bipole Search Programming Visit and Period (post implant standard of care)	Randomization Visit (21±7 days post Bipole Search Visit)	Crossover Visit (21±5 days post Randomizati on Visit)	Release Visit (21±5 days post Crossover Visit)	Randomi zation Periods 1&2 (duration 21±5 days)	Long Term F/U Period (duration 90 ±14 days)	End of Study Visit (90 ±14 days post Release Visit)	Unscheduled Visit
Device Programming Report	-	-	-	X	X	X	X	-	-	X	X
Determine Preferred Program	-	-	-	-	-	-	X	-	-	-	-
Lead Fluoro Imaging (per center's standard of care)	-	-	X	-	-	-	-	-	-	-	X**
Randomization	-	-	-	-	X	-	-	-	-	-	-
Adverse event assessment	-	-	X	X	X	X	X	X	X	X	X

Abbreviations: AM – morning, PM - afternoon

* In the event that the unscheduled visit is an additional Device Procedure

** In the event that Investigator suspects lead migration, per standard of care

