11.7. Randomization Visit (21±7 days post Bipole Search Visit)

Visit type: office

Goal: collect information from bipole search, determine effective program(s), retest paresthesia thresholds and distribution for selected programs, ensure that stimulation programs to be tested during Randomization Period 1 are programmed into the device and study patient understands the use of the system and requirements in order to ensure appropriate stimulation testing during this period spent at home.

Important: Randomization will only occur for subjects who received adequate therapy from one or more configurations tested since the Bipole Search Visit. For subjects that did not receive adequate therapy, there will be no randomization but subject will be asked to be followed up until the End of Study Visit. Those subjects may be programmed according to site's standard of care.

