11.9. Crossover Visit (21±5 days post Randomization Visit)

Visit type: office

Goal: This is the crossover visit. The purpose is to collect information from Randomization Period 1, determine effective amplitude(s) and program(s), retest paresthesia thresholds and distribution for selected programs, ensure that stimulation programs to be tested during Randomization Period 2 are programmed into the device and study patient understands the use of the system and requirements in order to ensure appropriate stimulation testing during this period spent at home.

11.10. *Randomization Period 2 (duration 21±5 days)*

Visit type: home; regular contact with study patient is recommended

Goal: offer study patient opportunity to test, for each given stimulation program, a number of different amplitudes, each over a duration of several days and report the outcomes

11.11. *Release Visit (21±5 days post Crossover Visit)*

Visit type: office

Goal: collect information from Randomization Period 2, determine effective amplitude(s) and program(s), retest paresthesia thresholds and distribution for selected programs, ensure that stimulation programs to be tested during Long term Follow up are programmed into the device and study patient understands the use of the system and requirements in order to ensure appropriate stimulation testing during this period spent at home.

11.12. *Long Term Follow-up Period (duration approximately 90 days)*

Visit type: home; regular contact with study patient is recommended

Goal: Subject will be encouraged to keep their preferred program. Further therapy optimizations are allowed in this period (physician discretion). Multiple programming visits may be done during this period (unscheduled).

11.13. *End of Study Visit (90±14 days weeks post Release Visit for subjects who completed crossover phase or 90±14 days post Bipole Search Phase for subjects who did not respond to 1kHz Bipole Search)*

Visit type: office

Goal: collect information on the outcome and various quality of life measures during Long-term Follow-up and conclude study patient's participation in the study.

11.14. *Unscheduled Visit*

An unscheduled visit is any visit that occurs during patient's participation in the study that is not aforementioned.

Visit type: office

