Goal: There are many reasons for an unscheduled visit, which include (but not limited to) loss of therapy, suspected lead migration, need for additional reprogramming, need for addressing a complaint or potential adverse event. Information will be collected from the previous period as well as the reason for the unscheduled visit, retest paresthesia thresholds and distribution for selected programs, and to plan and explain patient's continuation in the study. If imaging is required per standard of care to address suspected lead migration, it may be performed at an unscheduled visit.

11.15. *Study Completion*

Each patient's participation in the study will be considered complete upon completion of the End of Study Visit or upon patient withdrawal.

Upon completing participation in the study patients will continue to be followed per center's standard of care practice.

11.16. *Source Documents*

Table 11.16-1 summarizes all source data requirements for this protocol. Where copies of the original source document as well as printouts of original electronic source documents are retained, these shall be signed and dated by a member of the investigational site team with a statement that it is a true reproduction of the original source document.

Table 11.16-1: Source Documentation Requirements

Requirement	Disposition
Hospital records or clinical and office charts including the evidence of but not limited to inclusion/exclusion criteria, informed consent, procedures, and assessment of adverse events	Retain at center
Clinical evaluations (eg. questionnaires, drawings)	Retain at center
Programming Pre and Post-visit Reports (program settings, impedance measurements, program usage, battery voltage etc)	Retain at center
Lead Fluoro Images (if done per center's standard of care)	Retain at center
Diary data	Retain at center

12. Statistical Considerations

12.1. *Endpoints*

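### Section 10.2 lets a site withdraw a bipole-search non-responder for poor relief in a rescue period and then stops all data collection, although the synopsis, 8.2, 11.7 and 11.13 plan follow-up of non-responders to the End of Study Visit

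*Protocol*

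**What the plan says.** Section 10.2 (Withdrawal) gives a non-exhaustive list of reasons for which a subject might leave the study. One is "failure to achieve adequate pain relief during rescue period that follows the bipole search period". The section discourages withdrawal. It then forbids further data from being "collected after the point at which a patient has been withdrawn from the study or withdraws consent, for whatever reason". Removal by the study and withdrawal of consent therefore have the same consequence. Section 11.15 agrees: a patient's "participation in the study will be considered complete upon completion of the End of Study Visit or upon patient withdrawal".

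Four other places set the path of subjects in whom the bipole search fails:

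- Synopsis, method of assigning patients: "Subjects in whom an effective 1kHz bipole setting was not found will continue participation in the study for 3 month follow-up period", under the centre's standard-of-care stimulation.
- Section 8.2: "Subjects for whom an effective 1 kHz bipole setting was not found will continue participation in the study for 3 month follow-up period", again under standard of care.
- Section 11.7: "there will be no randomization but subject will be asked to be followed up until the End of Study Visit". These subjects may be programmed to the site's standard of care.
- Section 11.13 gives them their own End of Study window: "90±14 days post Bipole Search Phase for subjects who did not respond to 1kHz Bipole Search".

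In the readable part of Table 11.1-1, the row "Adverse event assessment" is marked for both the long-term follow-up period and the End of Study Visit.

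**The concern.** A subject who fails the bipole search and then gains too little relief in the rescue period has two paths in the same protocol. Under 10.2 the site may withdraw that subject, and no more data may be gathered. Under the synopsis, 8.2, 11.7 and 11.13 the same subject is to be followed for about three months. Two sites, or one site on two occasions, could treat like patients differently while each follows the protocol.

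The loss depends on outcome, because the bullet selects subjects by poor relief. What is then described at the End of Study Visit for non-responders can lean towards those who gained relief from standard-of-care programming. Scheduled adverse event assessment also ends early in subjects who have been implanted. An analysis plan can define sets and missing-data rules, but it cannot recover data that the protocol forbids collecting.

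**Working it through.** The protocol states no sample size calculation, and the point depends on none. The check is a comparison of sections.

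**1. Who can reach the rescue bullet?** The rescue period comes after the bipole search. The synopsis places the Randomization Visit at the end of that search, and 11.7 randomises there only subjects who received adequate therapy. A rescue step at that stage therefore most naturally concerns those who did not. This is an inference, because the readable text does not define the period.

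**2. Is the rescue period described elsewhere?** It does not appear in the synopsis follow-up schedule, in 8.2, in the visit descriptions 11.6 to 11.13, or in the readable rows of Table 11.1-1. Figure 8-1 is not shown and the table is incomplete, so a description may sit there. The point does not rest on a missing definition.

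**3. Do the sections agree for such a subject?**

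| Question | 10.2 and 11.15 | Synopsis, 8.2, 11.7, 11.13 |
|---|---|---|
| Status after poor relief in rescue | May be withdrawn | Planned follow-up continues, no exception stated |
| Data after that point | None may be collected | Collected to the End of Study Visit |
| Does standing consent matter? | No, both kinds of withdrawal are treated alike | Not addressed |

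**4. What is at risk in time?** The non-responder End of Study window is 90 − 14 = 76 to 90 + 14 = 104 days after the bipole search phase. The follow-up lost is that window minus the time already spent in rescue before withdrawal. The protocol does not give the length of the rescue period, so the subtraction cannot be done.

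**5. Which scheduled entries are at risk?** In the readable rows of Table 11.1-1:

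- adverse event assessment in the long-term follow-up period: 1
- adverse event assessment at the End of Study Visit: 1
- device programming report at the End of Study Visit: 1

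Total: 1 + 1 + 1 = 3. The outcome and quality-of-life measures that 11.13 names as the goal of the visit would go too, but their rows are not readable.

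**6. What is kept?** Section 10.2 requires that:

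- every enrolled subject is accounted for and the reason for withdrawal is reported;
- case report forms up to withdrawal and an end-of-study form are completed;
- open adverse events are closed or documented as unresolved.

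It allows use of data collected until then. Clinical care continues at the centre.

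**7. Does replacement repair the loss?** Section 10.2 replaces patients withdrawn before randomisation. That restores the number randomised, not the follow-up of the subject who left.

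**The case against.** The strongest reply is that there is no strict contradiction. The synopsis, 8.2 and 11.13 set a planned path, while 10.2 lists reasons why someone might leave it early, and the two normally coexist. The list is permissive, withdrawal is discouraged, and 11.7 says only that the subject will be asked to stay. Failing rescue is also narrower and later than failing the search. This stands as a limit on scope. It does not remove the inconsistency: use of the bullet is optional, but the stop on data that follows is not, and none of the four places makes an exception for poor relief.

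A second reply is that the failure is not hidden. For this bullet the recorded reason for withdrawal is itself the poor outcome, so a descriptive report can count these subjects. This stands. What is lost is their later course, not the knowledge that they failed.

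A third reply is that the unseen figure may settle the timing and criterion of rescue. This also stands, and it is why the point is confined to the conflict between readable sections.

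Some stronger readings are tempting but not supported:

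- *Every non-responder is removed.* The bullet reaches only those who also fail rescue, and only if the site uses it.
- *The crossover comparison is biased or loses pairs.* Non-responders are never randomised. Randomised subjects can meet the stop rule only through generic reasons such as physician discretion. A subject withdrawn before the second period has not received the second field type, so further assessment would not restore the pair.
- *A definite number of days is lost.* Any figure would need a rescue length borrowed from another period.
- *Section 20.4 is contradicted.* Its requirement to report device events to the end of the study can be read with 11.15, under which an individual's participation ends at withdrawal.

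**Conclusion.** The point holds in a narrow form, as a minor inconsistency. Section 10.2 permits withdrawal for inadequate relief in rescue and stops all data collection even where consent stands, while four other places plan follow-up of bipole-search non-responders to an End of Study Visit at 90±14 days. Non-responders who also fail rescue can lose their later outcome data and scheduled adverse event assessments, and the loss is selective by outcome.

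The size of the lost follow-up, and of any bias, cannot be derived from the protocol. The study is exploratory and descriptive, without a primary endpoint or hypothesis, so no confirmatory conclusion depends on this.

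The conclusion assumes that the rescue period concerns non-responders, and that Figure 8-1 and the unreadable part of Table 11.1-1 do not reconcile the sections. Whether consent would stand after such a withdrawal cannot be checked, because the consent pages are not available.

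**What to change.** Make two wording changes in 10.2:

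1. Delete the rescue-period bullet, or say that the rescue period is part of the standard-of-care follow-up that runs to the End of Study Visit.
2. State that, for implanted subjects who pass the lead-position check in 11.5, lack of relief or stopping the assigned programming is not withdrawal from the study. Scheduled outcome and adverse event assessments then continue unless the subject withdraws consent, is lost to follow-up or dies.

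The cost is an amendment to one bullet and one sentence, a few extra diary or visit records, and a check that the consent form covers continued collection. The visits themselves are already planned in 11.7 and 11.13. The second change goes further than the bullet, because it also narrows what physician discretion can end. A physician could still change or stop the programming, but that alone would no longer end data collection.
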